Relugolix will be provided at no cost by the study sponsor (i.e. Myovant Sciences). All medication supply will be stored and managed by Emory Investigational Drug Services Core. Medication delivery to enrolled subjects will be mediated by clinical research coordinators. Additionally, drug diaries will be reconciled by clinical research coordinators with oversite by the principal investigator [name].

Coronary Computed Tomography Angiogram (CCTA) Endpoint

As discussed in Aim 1 above, this study will utilize a state-of-the-art, validated non-invasive cardiac imaging, coronary CT angiogram, as the primary endpoint in this study. This imaging technique offers remarkable spatial resolution of coronary vasculature to test the primary hypothesis that ADT-mediated CV risk, namely from GNRHa, is driven by accelerated atherosclerosis and coronary disease. With modern imaging techniques, such as prospective triggering, radiation exposure to the patient is

Protocol Title: Mechanism and Predictors of Cardiotoxicity after Prostate Cancer Treatment: A Parallel Cohort and Randomized Trial Comparing Radiation Alone, Radiation plus Leuprolide, and Radiation plus Relugolix

[figure not shown]
minimized, as imaging is gated to be performed in only one phase of the cardiac cycle (rather than continuous during the entire cardiac cycle). Additionally, other measures, including limited field of view, limited scan length, and minimal tube voltage, will ensure that the additional radiation exposure sustained by CCTA in this study will remain around 3.2 mSv per patient (which is comparable or lower than the 3-7 mSv the average person receives annually from natural sources). Other cardiac imaging techniques, including catheter-based angiography or nuclear medicine studies, result in a substantially larger amount of radiation exposure to the patient (e.g. 21-41 mSv), and are therefore, less optimal to use as an endpoint in this study. Additionally, CCTA endpoints will allow to test both mechanism (e.g. involving accelerated coronary atherosclerosis and/or plaque instability), as well as help identify a novel imaging biomarker that may be used in clinical practice to identify those men at highest risk of an adverse CV outcome from ADT.

6. Procedures Involved

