Men with localized intact PCa, or non-metastatic recurrence following prostatectomy, and prescribed radiation therapy (XRT) with or without concomitant ADT will be consented and enrolled on this prospective trial. Eligible subjects are men > 18 years old diagnosed with non-metastatic PCa planning to undergo curative-intent therapy. Men with prior cardiac stent or bypass surgery will be excluded. Men with prior exposure to ADT will be excluded.

Each patient will undergo external beam XRT with or without concomitant ADT of 6-24 months duration. **For those men with National Comprehensive Cancer Network (NCCN)-defined unfavorable intermediate- or high-risk disease, or with biochemically recurrent PCa requiring salvage XRT plus ADT, each will be randomized 1:1 between injectable intramuscular or subcutaneous GNRHa depot (leuprolide 22.5 mg every 3 months, leuprolide 45 mg every six months) versus GNRH-antagonist (oral relugolix 360 mg loading dose followed by 120 mg daily).** Men with NCCN-defined low- or favorable intermediate-risk intact disease, or those with biochemically recurrent PCa requiring salvage XRT without ADT, will be treated with XRT alone. Each patient will provide consent for (1) pre-treatment and 12-month post-ADT prospective ECG-gated, contrast-enhanced CCTA and (2) peripheral blood banking at baseline and at 3-, 6-, and 12-months post-treatment (**Figure 5**).

Figure 5. Study Schema

ADT randomization will be created using preconstructed allocation sequences using maximal randomization (<https://ctrandomization.cancer.gov/tool/>). Patients will undergo a pre-randomization stratification based on Atherosclerotic Cardiovascular Disease (ASCVD) risk score (low/intermediate versus high). All principal investigators and co-investigators will be blinded to this randomization block. Lead statistician ([name]) and clinical research coordinators will have access to this allocation sequence.

Methods: As seen in above study schema, each patient in each cohort will undergo pre-treatment and 12-month post-ADT initiation coronary CT. Each patient will undergo a non-contrast CT scan using standard

Protocol Title: Mechanism and Predictors of Cardiotoxicity after Prostate Cancer Treatment: A Parallel Cohort and Randomized Trial Comparing Radiation Alone, Radiation plus Leuprolide, and Radiation plus Relugolix

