Based on current prostate cancer volume at Winship Cancer Institute, accrual is expected to be complete in 12 months. Specifically, approximately 40 new patients with localized intact or recurrent PCa eligible for XRT (with or without ADT) are seen at all Winship sites monthly. We predict an enrollment rate of 20% with a low dropout rate, given that the final blood draw and coronary CT will occur 12 months after treatment initiation, which corresponds to the time of first or second standard post-treatment follow up appointment after completion of therapy.

Clinical research coordinators will screen all prostate cancer radiation oncology providers (directed by PI [name]) for all eligible patients to enroll. Co-investigators will be responsible for consenting patients in radiation oncology clinic.

13. Recruitment Methods

Patients will be recruited from those seen at the Department of Radiation Oncology at Winship Cancer Institute (EUH, EUHM, ESJH, EPTC). A brief description of the study will be given verbally to the patients, followed by written informed consent, and any relevant supplemental material as needed. The patients will be given ample time to review the consent and a time for questions and answer will be provided.

Study Enrollment Procedures

A copy of the institution's IRB-approved informed consent document and written justification for any changes made to the informed consent for this protocol must be on file at the Online Collaborative Research Environment (OnCore, <https://oncore.emory.edu>) and available to the Emory University Office for Clinical Research) before any patients may enter. The Winship Cancer Center institution consent form must be reviewed and approved and all documents must be received (i.e., IRB approved documentation, IRB approved consent form, etc.).

Patient Registration

All patients entering this study will be registered with the Clinical Trials Office (CTO) at the Winship Cancer Institute, Atlanta, GA. The CTO is open Monday through Friday from 8am-5pm (EST). OnCore will be used to record information for all registered patients including their assigned patient ID.

Study personnel will notify Winship Central Subject Registration (WCSR) by email at [contact], once subject has been consented for a trial.

Email notification must be done within 24 hours after consent has been obtained and it will include scanned copies of:

- Signed patient consent form
- HIPAA authorization form

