- Emory Research Management System (ERMS; <https://erms.emory.edu>) Enrollment Fax Cover

The WCSR will enter the subject into the OnCore Research Management System, which is the system of record for Winship Cancer Institute Clinical Trials.

Eligible patients will be enrolled on study centrally at Winship Cancer Institute by the Study Coordinator. When all required test results are available, complete the eligibility checklist and provide the checklist and the supporting documentation to the IRB approved investigator for review and sign-off. Once the

Protocol Title: Mechanism and Predictors of Cardiotoxicity after Prostate Cancer Treatment: A Parallel Cohort and Randomized Trial Comparing Radiation Alone, Radiation plus Leuprolide, and Radiation plus Relugolix

investigator (sub-investigator, Co-Investigator) has signed the eligibility checklist, enrollment may proceed. Oncore and ERMS must be updated to reflect eligibility and on treatment status.

14. Withdrawal of Participants

Participation in the study should continue until one of the following criteria applies:

- Intercurrent illness that prevents delivery of planned radiation therapy or ADT
- Unacceptable treatment-related adverse event(s), including patient death
- Withdrawal of informed consent (subject's decision to withdraw for any reason)
- Noncompliance with treatment plan, including delays to treatment or acquisition of additional diagnostic imaging that significantly exceeds the proposed timeline of study events
- General or specific changes in the patient's condition that render the patient unacceptable to receive further treatment in the judgment of the investigator
- Lost to follow up. In the event of a patient's withdrawal, the Investigator will make every effort to complete the End of Treatment/follow-up procedures specified in the Schedule of Events.

15. Risk to Participants

Radiation therapy +/- hormone therapy (either GNRHa or relugolix) are FDA-approved, guideline-supported standard treatments for prostate cancer. There is no additional risk associated with treatment on study, including the randomized portion of treatment (i.e. GNRHa with Lupron/Trelstar and Relugolix are acceptable ADT options for men with prostate cancer undergoing radiation therapy). There is no additional risk associated with blood draws (which will correspond to blood draws taken at standard clinical intervals to minimize additional appointment or peripheral venous sticks).

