Informed consent is to be obtained prior to commencing any research procedures. Patients will be recruited from those seen at the Department of Radiation Oncology at Winship Cancer Institute (EUH, EUHM, ESJH, EPTC), either at the time of initial consultation or pre-treatment follow up appointment. A brief description of the study will be given verbally to the patients by the treating physician (and co-investigator of trial). This will be followed by written informed consent. The patients will be given ample time to review the consent and a time for questions and answer will be provided. The co-investigator may choose to consent the patient with or without presence of the clinical research coordinator. Once consent has been obtained, the treating physician will notify by email the contact principal investigator ([name]) and clinical research coordinators for final screening, enrollment, and (if needed) randomization.

A study investigator shall seek such consent only under such circumstances that provide the prospective patient opportunity to consider whether or not to participate and that minimizes the possibility of coercion or undue influence. The information given to the patient, or the representative, shall be in a language understandable to the subject or representative. The informed consent document may not include any exculpatory language through which the subject or representative is made to waive any of the subject's legal rights or releases, or appears to release the investigator, the sponsor or the institution from liability for negligence.

Non-English-Speaking Participants

A certified translator/interpreter will be present during the consenting process and all questions and concerns will be answered by the treating physician.

A Short Form in that specific language will be used. A certified translator/interpreter will be present during the consenting process and this will be documented. We will use what's available on Emory IRB website. For the languages that are not available, we will have the short form translated to that language and

Protocol Title: Mechanism and Predictors of Cardiotoxicity after Prostate Cancer Treatment: A Parallel Cohort and Randomized Trial Comparing Radiation Alone, Radiation plus Leuprolide, and Radiation plus Relugolix

submit the IRB for review and approval prior to use. Process to Document Consent in Writing: Winship SOP 2.1: "Obtaining Informed consent for Interventional clinical trial" will be followed.

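### The clinical research coordinators can see the preconstructed allocation sequence, and they also screen, enrol and take part in randomising the patients

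*Combined protocol and SAP*

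**What the plan says.** Section 6 (Procedures Involved) has the ADT randomisation, 1:1 and stratified by ASCVD risk in two levels, run from sequences prepared in advance. It then says who may see them. On one side, "All principal investigators and co-investigators will be blinded to this randomization block". On the other, the lead statistician and "clinical research coordinators will have access to this allocation sequence".

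Other sections describe what coordinators do:

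- Section 12 (Local Number of Participants): "Clinical research coordinators will screen all prostate cancer radiation oncology providers" to find eligible men, under the direction of a principal investigator.
- Section 13 (Patient Registration): "Eligible patients will be enrolled on study centrally at Winship Cancer Institute by the Study Coordinator".
- Section 22 (Informed Consent): after consent, the treating physician emails the contact principal investigator and the "clinical research coordinators for final screening, enrollment, and (if needed) randomization".
- Section 5 (Study Intervention): "Medication delivery to enrolled subjects will be mediated by clinical research coordinators".

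The plan also contains controls. Co-investigators, who are blinded to the sequence, obtain consent (sections 12 and 22). Before enrolment the study team must "provide the checklist and the supporting documentation to the IRB approved investigator for review and sign-off" (section 13). Central registration is told of each consent, and "Email notification must be done within 24 hours after consent has been obtained" (section 13).

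**The concern.** Concealment before assignment is a different matter from blinding after it. The trial is open-label (section 1) and run at one institution (section 23), so concealment is one of the main protections of its only randomised contrast, GNRHa versus relugolix. Section 6 recognises this by keeping investigators from the sequence, but it leaves out the staff who find and enter the patients.

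A coordinator who knows the next assignment can influence which men are flagged, when a file is completed, and in what order men are entered. This needs no bad faith. The arms differ visibly (injection versus tablet, with relugolix supplied free), and the protocol itself describes relugolix as reducing cardiac risk, so well-meant steering is plausible. Its direction is unknown.

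Stratification on two ASCVD levels and adjustment for covariates such as age and statin use (section 6, Aim 1 analysis plan) remove only the part of an imbalance that those variables capture.

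**Working it through.** **Step 1: who knows what, and who does what.**

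| Step | Who acts | Access to the sequence (section 6) |
|---|---|---|
| Finding eligible men (section 12) | Clinical research coordinators, directed by a principal investigator | Coordinators yes; principal investigator no |
| Consent (sections 12, 22) | Co-investigators; a coordinator may be present | Co-investigators no; coordinators yes |
| Eligibility sign-off (section 13) | Investigator | No |
| Enrolment (section 13) | Study Coordinator | Not stated under that title |
| Final screening, enrolment, randomisation (section 22) | Contact principal investigator and clinical research coordinators are notified | Principal investigator no; coordinators yes |

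The overlap rests on sections 6, 12 and 22, which use the same job title. It stands even if the Study Coordinator of section 13 is someone else. The documents do not say whether the individuals are the same.

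**Step 2: do the controls close the gap?** Eligibility sign-off tests whether a man qualifies, not whether his entry was timed. The 24-hour email fixes the date of consent, but enrolment follows later, once test results are in and the checklist is signed. The order of randomisation can therefore differ from the order of consent. No section describes envelopes, web or telephone release, or single disclosure, and none ties release of an assignment to registration.

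**Step 3: do coordinators need the sequence?** They deliver medication, so they need each man's assignment once it is made. Nothing shows a need for it beforehand.

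**Step 4: an illustration of size.** The plan gives no figure for this. Inputs from section 6 (Power): 30 men per arm, SD of change 30 mm³, target difference 20 mm³. Assumed inputs:

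- k = 1 to 3 places exchanged per arm, all in the same direction.
- d = 0.25 to 1 SD difference in expected 12-month change between the men exchanged.
- Two-sided alpha of 5%, because the plan states neither alpha nor sidedness.

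Each exchange moves one arm's mean up and the other's down by d × 30 / 30 mm³, so

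shift = 2 × k × (d × 30) / 30 = 2kd mm³.

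The standard error is 30 × √(2/30) = 7.75 mm³. By the normal approximation, the type I error is P(Z > 1.96 − shift/SE) + P(Z < −1.96 − shift/SE).

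| k | d (SD) | Shift (mm³) | Share of 20 mm³ | Type I error |
|---|---|---|---|---|
| 1 | 0.25 | 0.5 | 2.5% | 5.05% |
| 2 | 0.5 | 2 | 10% | 5.8% |
| 3 | 1 | 6 | 30% | 12.1% |

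The last row requires staff to predict the 12-month change in plaque by a full SD. It is the upper bound of this illustration, not a forecast.

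**The case against.** The strongest reply is that the text shows a missing procedure rather than an actual loss of concealment. Someone has to carry out the randomisation that section 22 passes to coordinators, and access to the sequence may mean no more than looking up the next line when a man is ready. That is possible, but section 6 grants access to the sequence without limit, and seeing even one assignment before enrolment is enough to defeat concealment. If practice is already single release after enrolment, the change simply records it.

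A second reply is that the opening is small. A blinded principal investigator directs screening, and blinded investigators take consent and confirm eligibility. Section 12 expects 40 × 20% = 8 enrolments a month over three cohorts. If the cohorts fill equally, about 8 × 60/90 = 5.3 of these are randomised each month, or 2 to 3 per stratum if the strata are equal. Reordering needs two men pending together in one stratum with different upcoming assignments. This stands as an argument about size. It does not cover selective flagging, which needs no second man waiting.

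Third, the inputs to the illustration are assumed, and several push it upwards. Exchanges would usually fall within an ASCVD stratum, which narrows the predictable difference. Section 8 keeps scan findings blinded until the 12-month scan, and although that section concerns disclosure to participants, nothing shows that coordinators would see baseline plaque. This also stands: the large case is unlikely, and the concern does not depend on it.

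**Conclusion.** The concern holds. Section 6 gives sequence access to a group that sections 12 and 22 also charge with screening and with enrolment and randomisation, and no section restricts that access. This is certain as a reading of the text. What is not known is whether the same individuals hold both roles, how access works in practice, and the size and direction of any bias.

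Under the stated assumptions the shift is modest in the low and middle cases (0.5 and 2 mm³) and material only in the extreme one (6 mm³). The point should be fixed because it affects the trial's only randomised contrast, because selection bias cannot be repaired with confidence afterwards, and because prevention is cheap. It does not by itself invalidate the design.

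**What to change.** Replace the sentence on access in section 6 with wording such as:

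> *Only the lead statistician, or other staff not involved in screening or enrolment, holds the allocation sequence. Each assignment is released singly to the coordinator, and only after consent, the signed eligibility checklist, central registration and the ASCVD stratum are recorded.*

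An existing electronic system can do this if it supports single release. Otherwise the statistician or a delegate releases on request and logs date and time. If the team prefers to keep the person leading the analyses out of daily operations, a delegate outside screening and enrolment can take the task.

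The cost is one amended sentence, a release log and about 60 releases (30 per randomised arm). The change needs IRB approval before use (section 19). There will be a short wait per randomisation, and because release depends on registration it will follow the registering office's weekday hours (section 13). No new system is required, since the statistician already has the sequence, and sample size and treatment are unaffected.

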coronary artery calcium (CAC) imaging protocol for coronary calcium quantification prior to the acquisition of the CCTA. CAC images will be obtained using prospective ECG-triggering at 70% of the R-R interval, using tube voltage of 120 kV and an automated tube current modulation and minimum slice collimation (0.6 mm). Images will be reconstructed in 3 mm slice thickness at 3 mm intervals. Following CAC scan, contrast-enhanced CCTA will be performed using an ECG-gated, single-beat acquisition scan to include 30-80% of the R-R interval. Scanning will extend from the tracheal bifurcation to 2 cm below the left ventricular apex; 0.5 mm detector collimation will be used.

Additionally, peripheral blood will be drawn and stored in our established biorepository (under protocol WINSHIP5179-20) at the following intervals: pre-treatment, and 3-, 6-, and 12-months post-ADT initiation. Further details regarding analysis plan of peripheral blood below in Aims 2 and 3.

Aim 1.1: To determine the relationship between ADT (i.e. GNRHa versus relugolix) and accelerated coronary plaque development and/or rupture in PCa men, all contrast enhanced CCTA images will be analyzed using a commercially-available, validated artificial intelligence-guided imaging analysis service (HeartFlow, Inc, Mountain View CA). Multiplanar reconstructed images will be assessed for the presence, volume, and qualitative composition (e.g. total, calcified, non-calcified, mixed) of atherosclerotic plaque for each coronary artery segment. Luminal stenosis will be graded on an ordinal scale 0-100%. CCTA scans pre- and 12 months post-treatment will be compared. We hypothesize that ***men receiving GNRHa will be at increased risk of total plaque volume increase compared with men receiving relugolix or no ADT.***

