Analysis Plan: We will measure coronary plaque volume using CCTA images at both baseline and 12-months post-treatment initiation. The primary endpoint will be (1) total coronary plaque volume (continuous). Secondary endpoint will be non-calcified coronary plaque volume (continuous). Other outcome measures include (1) calcified plaque volume (continuous), (2) low-attenuation plaque volume (continuous), (3) coronary artery calcification score (continuous), and (4) coronary vessel stenosis (ordinal). The change in endpoint metrics between baseline and 12-month will be estimated for leuprolide versus relugolix versus no ADT. Data transformation to fit statistical assumptions will be done as needed. In addition, we will implement multivariable models that control for potential confounders (e.g. age, statin medication use) using general linear regression and/or logistic regression.

Power: We hypothesized that there will be significantly greater total plaque burden (i.e. summation of total plaque volume of all major coronary territories) increase from baseline to month 12 following GNRHa versus no ADT or relugolix. Using a standard deviation of 30 mm³ for the change in total plaque volume from scans obtained at two time points approximately 12 months apart in the study, 60 participants (30 in each comparative treatment arm) with both baseline and month 12 CCTA would provide 80% power to detect a difference of ≥ 20 mm³ in the change in total plaque volume [$P(X>Y) 0.72$] from baseline to 12 months.

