Analysis Plan: The correlation among baseline genomic biomarkers, inflammatory biomarkers, and proteomic biomarkers will be described using Spearman Correlation Coefficient for all patients and by treatment group separately. The association of genomic alterations with CV injury metrics (as defined in Aim 1) will be handled by similar statistical strategy as in Subaim 1.2. Additionally, the association of genetic aberrations with peripheral immune responses (as in Aim 2) will be carried out by similar statistical strategy as in Aim 2.

Other statistical considerations:

Safety Population: All patients receiving at least one dose of GNRHa or Relugolix (for parallel randomized arms) or radiation alone (for parallel single cohort arm) will be considered evaluable for safety analyses.

Intent-to-Treat Population: Patients who are evaluable for safety and who are furthermore evaluable at 12-month CCTA assessment will be considered evaluable for correlative biomarker analyses.

Safety Analysis: All AEs experienced data will be described by summary statistics. Adverse events will be assessed according to CTCAE version 5.0 and will be evaluated by grade, attribution, and organ class. Adverse event listings and tabulated summaries of categorized AEs will be generated for all patients collectively and will be summarized by arms. Vital signs and laboratory data will be summarized for changes over time on study.

Stopping Rule: The two ADT test agents are FDA-approved drugs that are used in clinical practice, and hence no stopping rule for safety is in place officially.

7. Data Specimen Banking

To achieve Aims 2 and 3 discussed above, peripheral blood specimens will be collected longitudinally four times for each enrolled patient (i.e. pre-treatment, 3 months, 6 months, 12 months).

Draw 1 (pre)	Draw 2 (3mo)	Draw 3 (6mo)	Draw 4 (12mo)
Pre-ADT	2-4 months post-ADT initiation	6-8 months post-ADT initiation	12-15 months post-ADT initiation

The blood is collected and processed according to the standard operating practices and regulatory parameters of the Winship biorepository and under the guidance of a board-certified pathologist.

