receive report of the image findings (i.e. scan #1 and #2). These scans are guideline-concordant cardiac screening tests, and findings may be used to appropriately manage patients with regards to his cardiovascular health. As all scans are blinded before completion of #2 scan (i.e. 12 months after enrollment), no scan #1 image findings will be disclosed to patients until after the 12 month study period. Of note, all CT images will be interpreted regarding coronary artery (e.g. stenosis, calcification) and epicardial adipose tissue findings only; any pulmonary, mediastinal, or osseous findings will not be interpreted by the cardiac radiologist.

Blood bank analyses (for Aims 2 and 3) are for research purposes only and will not be disclosed to patients during or after completion of the study period.

9. Study Timelines

Each patient will be enrolled on study for a total of ~12 months, which includes time from pre-treatment coronary CT and blood draw, to 12-month coronary CT and final blood draw. Each patient will undergo XRT +/- ADT for management of localized prostate cancer in the interim.

Based on current volume of newly diagnosed localized prostate cancer eligible for definitive XRT across all Winship Cancer Institute sites, we anticipate to complete accrual of the study (i.e. 3 treatment cohorts, n=30 in each arm; see Figure 5 Study Schema) within 12 months after study opening. Study endpoints for Aim 1-3 (i.e. imaging findings, blood analyses) will be completed on a rolling basis, and thus, we anticipate completion of data acquisition within 24 months after study opening.

Completion of this mixed-methods research will involve a robust multidisciplinary team across Winship, including Radiation Oncology (Drs. [name] and [name]; leading the accrual of patients to trial), Cardiology/Cardiac Imaging (Drs. [name], [name], [name]; leading the coronary CT interpretation on study for Aim 1), Hematology and Medical Oncology ([name]; leading the laboratory analyses of peripheral blood for Aims 2-3), and Biostatistics ([name]; leading all statistical analyses for Aims 1-3).

Projected funding start date: 12/1/2021

Projected funding end date: 11/30/2023

Timeline for Completion of Proposed Research	Months	3	6	9	12	15	18	21	24
Aim 1. Effect of leuprolide versus relugolix on coronary plaque development using non-invasive cardiac imaging									

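### The second coronary CT is timed from a date the no-ADT cohort does not have, so the scan-to-scan interval can differ between the ADT arms and that non-randomised cohort

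*Combined protocol and SAP*

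**What the plan says.** Section 6 (Procedures Involved) has each patient consent to "pre-treatment and 12-month post-ADT prospective ECG-gated, contrast-enhanced CCTA", and its Methods paragraph states that "each patient in each cohort will undergo pre-treatment and 12-month post-ADT initiation coronary CT". Section 21 (Economic Burden) also counts from ADT initiation. Section 6 further says that men not needing ADT "will be treated with XRT alone". For men who do receive ADT, the description is "external beam XRT with or without concomitant ADT of 6-24 months duration", with no rule on the order of, or gap between, the two starts.

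Other places use other anchors:

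- Section 6, Aim 1.1: "CCTA scans pre- and 12 months post-treatment will be compared", without saying whether the start or the end of treatment is meant.
- Section 6, Aim 1 Analysis Plan: "baseline and 12-months post-treatment initiation". Section 12 also counts from treatment initiation. Neither says which treatment counts.
- Section 8: "i.e. 12 months after enrollment".
- Section 9: roughly 12 months on study, described as running from the pre-treatment CT to the 12-month CT.

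The only numeric month-12 window is in the section 7 blood-draw table, "12-15 months post-ADT initiation". Section 14 allows withdrawal when delays to treatment or imaging go well beyond the planned timeline, but gives no number.

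The Aim 1 Analysis Plan compares the baseline-to-12-month change across leuprolide, relugolix and no ADT. Age and statin use are its example covariates.

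**The concern.** The primary endpoint is a change between two scans, and plaque change accrues with time. A longer interval in one group shows up as a larger change whatever the drug does. The timing rule cannot be followed for the 30 radiation-alone men, so staff must choose a substitute date. The other sections offer several.

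This reaches the primary hypothesis. Both the Aim 1.1 hypothesis and the Power paragraph set GNRHa against no ADT as well as against relugolix. Because the no-ADT cohort is not randomised, nothing in the design balances its intervals against those of the ADT arms. Section 6 also makes evaluability at the 12-month CCTA a condition for the correlative biomarker analyses, which is hard to apply without a common time zero and a window.

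**Working it through.** **Inputs from the Power paragraph, section 6.** SD of change 30 mm³, target difference 20 mm³, 30 men per arm, stated power 80%. Alpha and sidedness are not stated there; I take alpha as 0.05.

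**The plan's own figure.** With SD 30 and difference 20, a one-sided 0.05 test gives 81.8% (t test) or 80.0% (simulated Mann-Whitney), which matches the stated 80%. Two-sided, power is 73.3% (normal approximation), 71.9% (t) or 69.0% (Mann-Whitney), which does not. I use the two-sided normal figure below as the reference.

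**Inputs the documents do not give.** The plaque growth rate and the between-group gap in mean interval are both assumed. I take 20–60 mm³ per year, with 10 as a low check, and gaps of 1, 1.5 and 3 months. If one group's scans were spread evenly over months 12–15 and the other's all fell at month 12, the gap would be 13.5 − 12 = 1.5 months. A 3-month gap needs every man in one group at month 15 and every man in the other at month 12.

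**Spurious difference** = rate × gap / 12, with its share of 20 mm³ in brackets:

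| Rate (mm³/year) | 1 month | 1.5 months | 3 months |
|---|---|---|---|
| 10 | 0.8 (4%) | 1.25 (6%) | 2.5 (12.5%) |
| 20 | 1.7 (8%) | 2.5 (12.5%) | 5.0 (25%) |
| 40 | 3.3 (17%) | 5.0 (25%) | 10.0 (50%) |
| 60 | 5.0 (25%) | 7.5 (37.5%) | 15.0 (75%) |

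**Effect on the test.** The standard error of a 30-versus-30 difference is 30 × √(2/30) = 7.75 mm³. For a nominal two-sided 5% test:

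| Spurious difference (mm³) | Rejection rate under a true null | Power if it acts against the hypothesis | Power if it acts with it |
|---|---|---|---|
| 0 | 5.0% | 73.3% | 73.3% |
| 2.5 | 6.2% | 61.8% | 82.8% |
| 5.0 | 9.9% | 49.1% | 89.8% |
| 7.5 | 16.2% | 36.5% | 94.4% |

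**Direction.** Suppose no-ADT men are timed from enrolment and ADT men from the first dose. ADT intervals then tend to be longer, and the GNRHa-minus-no-ADT difference is inflated. Suppose instead that no-ADT men are timed from the end of radiation, which is one reading of the Aim 1.1 wording. Their intervals lengthen and the difference shrinks. The documents do not settle which applies.

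**Randomised contrast.** Both arms count from ADT initiation, so the common effect is added scatter. A uniform 3-month window has SD 3/√12 = 0.87 months. At 20–60 mm³ per year that is 1.4–4.3 mm³, and √(30² + 4.3²) = 30.3, so the SD rises by about 1% at most.

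**The case against.** The best reply is that the intent is clear. Section 9 describes about 12 months from first scan to second for every patient, and the Power paragraph assumes scans about 12 months apart. Section 14 gives a ground for withdrawing men whose treatment or imaging runs far off schedule. The covariates are introduced only as examples, so the interval is not excluded. The study schema (Figure 5) is not reproduced in the text available, and the Schedule of Events that section 14 mentions does not appear there either. A scan window could sit in one of them. All of this stands. It limits the likely size of an imbalance and means that the absence of a window can be asserted only for the visible text. It does not supply a date for the no-ADT cohort or reconcile the anchors.

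A reader might infer that ADT men are scanned up to three months late while no-ADT men are scanned on time. The documents do not support that. The 12–15 month window belongs to the blood draw, and section 7 applies the draws to every enrolled patient. Section 12 places the final draw and the second scan at the same point for everyone, so lateness could be shared.

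A reader might also infer that the leuprolide-versus-relugolix comparison is biased. The documents do not show this: it would need lead time or lateness to differ by arm.

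**Conclusion.** The point holds for contrasts with the no-ADT cohort. A stated timing rule for the primary endpoint cannot be applied to one of the three groups, the sections disagree on the alternative, and the raw-change analysis has no named protection against unequal intervals.

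What follows is a possible imbalance, not a demonstrated one. On assumed growth of 20–60 mm³ per year, a 1.5-month difference in mean interval gives 2.5–7.5 mm³, and the 3-month figure of 5–15 mm³ should be read as a worst case. Neither size nor direction can be derived from the documents. The randomised contrast is little affected. The change is worth making because it is cheap and the affected comparison is part of the primary hypothesis.

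**What to change.** Define one index date that exists in every cohort. Two options fit the text:

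- The baseline scan date, as section 9 implies. This equalises the intervals directly but lets time since treatment start vary with the lead.
- The start of first study treatment: first ADT dose or, without ADT, first radiation fraction. This fixes time since treatment start but leaves the interval dependent on the lead.

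Use the chosen date in section 6 (consent sentence, Methods, Aim 1.1, Analysis Plan), the section 7 draw table, and sections 8, 9, 12 and 21. Set a maximum lead for scan 1 before treatment and a symmetric window around month 12 for scan 2.

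In the Aim 1 model, include the actual scan-to-scan interval or analyse annualised change, and keep raw change as a sensitivity analysis.

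The cost is protocol wording and one variable computed from the two scan dates. The downside is that the adjustment assumes roughly linear change over the window, and it leans harder on that assumption if intervals barely overlap between groups. The windows help only scans not yet taken; the interval adjustment should be specified before the data are analysed.
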